A phase 1, FIH, open-label, dose escalation study ([1351.1](#)) is ongoing to characterize the safety, tolerability, pharmacokinetics, and pharmacodynamics of cIV doses of AMG 420 in subjects with RRMM. AMG 420 is administered as a cIV infusion for 4 consecutive weeks via an indwelling central IV line. After a 2-week treatment-free

period, the subjects receive up to a total of five 4-week on/2-week off courses. If subjects experience continued benefit, up to 5 more courses may be given.

Data from 35 subjects (up to 800 µg/day) were available at the time of data snapshot (22 May 2018). Subjects were treated at doses ranging from 0.2 µg/day to 800 µg/day. In general, AMG 420 was well tolerated. All 35 subjects (100%) had adverse events; 32 of 35 subjects (91.4%) had adverse events grade ≥ 3. The most frequent adverse events were lymphocyte count decreased (21 subjects, 60.0%); anemia (12 subjects, 34.3%); white blood cell count decreased (12 subjects, 34.3%); pyrexia (11 subjects, 31.4%); and CRS (10 subjects, 28.6%). Infections and infestations occurred in 23 subjects (65.7%), most notably device related infections in 7 subjects (20.0%). Thirty-three of 35 subjects (94.3%) had an adverse event considered drug-related by the investigator. The most frequent drug-related adverse events (> 20%) were lymphocyte count decreased (21 subjects, 60.0%) and CRS (10 subjects, 28.6%). Drug-related grade 3 and grade 4 adverse events occurred in 10 subjects (28.6%) and 17 subjects (48.6%), respectively. The most frequent drug-related grade 3 and grade 4 adverse events were lymphocyte count decreased, with 6 subjects (17.1%) reporting grade 3 events and 14 subjects (40.0%) reporting grade 4 events. No drug-related grade 5 events were reported in this study. Serious adverse events were reported in 17 subjects (48.6%). The most frequent serious adverse events were device-related infections, pneumonia, and cytokine release syndrome (CRS) in 3 subjects (8.6%) each. Most subjects reporting serious adverse events had grade 3 adverse events (12 subjects, 34.3%). Drug-related serious adverse events were CRS in 3 subjects (8.6%), and peripheral motor neuropathy, generalized edema, and pyrexia in 1 subject (2.9%) each. Two dose-limiting toxicities (DLTs) were reported in the 800 µg/day cohort; 1 grade 3 CRS and 1 grade 3 peripheral motor neuropathy.

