#### 5.1.1 Phase 1b (Monotherapy Dose Confirmation)

In phase 1b, approximately 10 subjects will be treated at the 400 µg/day dose (comprising cohort 1). Approximately 10 subjects will be treated at the 600 µg/day dose level (cohort 2).

The dose level review team (DLRT) will convene and review all available safety, laboratory, and PK data at the following scheduled time points:

- After at least 10 subjects in phase 1b cohort 1 (400 µg/day dose level) have had the opportunity to complete the 4-week infusion period of the first treatment cycle: On the basis of this review, the DLRT will make a recommendation regarding the initiation of phase 1b cohort 2 (600 µg/day dose level).
- After at least 3 subjects with EM relapsed disease in phase 1b cohort 1 (400 µg/day dose level) have had the opportunity to complete the 4-week infusion period of the first treatment cycle: On the basis of this review, the DLRT will make a recommendation regarding the appropriateness of continued enrollment of subjects

with EM relapsed disease in phase 1b cohort 2 (600 µg/day dose level). Please note that enrollment of subjects with EM relapsed disease in phase 1b cohort 2 will not be allowed until this safety review of the first 3 subjects with EM disease is completed by the DLRT.

- After the first 3 subjects have been dosed with AMG 420 at 600 µg/day for the full 4-week infusion cycle in phase 1b cohort 2.

In phase 1b, the safety data will be reviewed on an ongoing basis and enrollment may be terminated at any time. To further reduce the risk of overdose to ongoing and future subjects, protocol-defined enrollment holding rules will be used. These rules are based on a modified Toxicity Probability Interval (mTPI) (Ji et al, 2010) where the target TPI is a DLT probability from 20% to 33% and the overdose TPI is > 33% DLT probability. Enrollment to the ongoing dose level/schedule will be paused per the rules in [Table 5-1](#) during enrollment into phase 1b cohorts 1 and 2.

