**Table 5-1. Rules for Holding Enrollment in Phase 1b**

Number of Dose-limiting Toxicities	≥ 2	≥ 3	≥ 4
Number of Treated Subjects	≤ 4	≤ 6	≤ 8

If the rules for pausing enrollment are met, no further enrollment to the respective dose level/schedule will be allowed until after a careful review of all safety data by the DLRT. Additionally, enrollment will not resume until the protocol has been amended to include additional safeguards for subject safety (eg, modifications to dose level and schedule).

Subjects with EM disease will be able to enroll into cohort 2 after the safety evaluation is complete for 3 subjects with EM disease treated at 400 µg/day.

For definition of the DLT evaluation period and DLT-evaluable subject refer to [Section 7.4.1](#). For details on the mTPI model see [Section 10.3](#).

An investigator will review efficacy data and assess outcomes in accordance with IMWG criteria. Investigator assessments will be used for primary efficacy analysis.

The overall study design is described by a study schema in [Section 2.1](#). The endpoints are defined in [Section 4.1](#).

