#### 5.4 Justification for Investigational Product Dose (AMG 420)

The primary purposes in phase 1b are to 1) confirm the safety and tolerability of the 400 µg/day dose level in subjects with or without extramedullary (EM) disease and 2) establish the safety and tolerability of the 600 µg/day dose level.

The rationale for dosing in this study is based on the observations and experiences with AMG 420 in the separate FIH study conducted by BI (1351.1), which suggests that a cIV administration is safe and has the potential to induce durable remissions in patients with RRMM. This BI 1351.1 study has identified the 400 µg/day dose level as a preliminary safe and effective dose, as this dose was well tolerated in n = 3 subjects, whereas 2 of 3 subjects treated at the 800 µg/day dose experienced DLTs. The 600 µg/day dose level was not evaluated in the FIH study. Subjects may benefit from higher exposures than are achieved at the 400 µg/day dose level; thus, safety and tolerability of the 600 µg/day dose level may be evaluated in this phase 1b study. The DLRT will convene and review all available safety, laboratory, and PK data from all subjects treated in phase 1b cohort 1 at the 400 µg/day dose before recommending evaluation of the 600 µg/day dose (phase 1b cohort 2). If the DLRT recommends the 600 µg/day dose to be safe and well-tolerated after reviewing the phase 1b cohort 2 data, the sponsor may propose changing the recommended phase 2 dose to 600 µg/day on the basis of interim data analyses.

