#### **7.4 Dose Modification**

##### **7.4.1 Dose-cohort Study Escalation/De-escalation and Stopping Rules**

The DLT evaluation period (ie, DLT-evaluable period) will be the 4 weeks on AMG 420 treatment within the first treatment cycle, starting on day 1 (start of infusion). The DLT evaluation period may also be extended to assess events starting within the window in case the DLT definition is time dependent.

Treatment in AMG 420 cycle 1 will be considered complete and the subject will be DLT evaluable if the subject has completed the DLT evaluation period or experienced a DLT any time during the DLT evaluation period. A subject will be non-DLT evaluable if he/she drops out before completion of the DLT-evaluable period for reasons other than a

DLT. All available safety data for subjects who are non-DLT-evaluable will still be evaluated and considered in DLRT decisions (see also [Section 10.4.1.1.1.1](#)).

See [Section 5.2.1](#) for description of replacement of subjects.

A DLT will be defined as any of the events described below occurring in a subject during the DLT evaluation period unless clearly attributable to causes other than treatment with AMG 420. The CTCAE version 5.0 (see [Section 12.4](#)) will be used to assess toxicities/adverse events with the exception of CRS and TLS (see [Section 7.4.2.1.2.5](#) and [Section 12.12](#) for grading criteria of CRS and TLS, respectively).

- Death not clearly due to the underlying disease or extraneous causes.

Non-hematologic DLTs:

- Non-hematological adverse event grade 3 or higher, EXCEPT:
  - infection responding to antibiotic/anti-infective treatment within 48 hours
  - grade 3 fatigue or asthenia
  - grade 3 headache resolving to  $\leq$  grade 2 within 72 hours
  - grade 3 insomnia resolving to  $\leq$  grade 2 within 7 days
  - grade 3 fever resolving to  $\leq$  grade 2 within 72 hours
  - grade 3 nausea, vomiting, or diarrhea responding if successfully managed with optimal medical support and resolved within 72 hours
  - laboratory parameters of grade  $\geq$  3, not considered clinically relevant, and improved to grade  $\leq$  2 within 72 hours

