- Any subject meeting the criteria for Hy's Law case (ie, severe drug-induced liver injury [DILI]) will be considered a DLT. A Hy's Law case is defined as: AST or ALT values of  $\geq 3 \times$  ULN AND with serum TBIL level of  $> 2 \times$  ULN or international normalized ratio (INR)  $> 1.5$  without signs of cholestasis and with no other clear alternative reason to explain the observed liver-related laboratory abnormalities (see [Section 7.4.3](#) for hepatotoxicity management and [Section 12.7](#) for further explanation of Hy's law case and management of hepatic function).

Hematologic DLTs:

- febrile neutropenia grade 4
- febrile neutropenia grade 3 unless responding to antibiotic/anti-infective treatment within 48 hours
- grade 4 neutropenia lasting more than 5 days, grade 4 thrombocytopenia lasting more than 7 days, grade 3 thrombocytopenia with hemorrhage or required platelet transfusion, or grade 4 anemia in the absence of detectable multiple myeloma as it may reflect a marrow toxic effect of AMG 420

The dosing schedule is described in the Schedule of Activities ([Section 2.2](#)).

---

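### Table 5-1 counts subjects still inside the DLT window, so 2 DLTs in the first 3 at 600 µg/day need not force a pause if starts are quick and DLTs are known late

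*Protocol*

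**What the plan says.** Protocol 5.1.1 lists three scheduled DLRT reviews; the synopsis, Appendix 3 (12.3) and SAP 3.1 repeat them.

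- The review of cohort 1 leads to a recommendation on opening cohort 2.
- The review of subjects with extramedullary (EM) disease carries a bar: their enrollment into cohort 2 "will not be allowed until this safety review of the first 3 subjects with EM disease is completed by the DLRT".
- The review within cohort 2 takes place "After the first 3 subjects have been dosed with AMG 420 at 600 µg/day for the full 4-week infusion cycle". It has no stated consequence and no bar on starts.

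The binding rule is Table 5-1 (SAP Table 1): pause at 2 or more DLTs with up to 4 subjects, 3 or more with up to 6, and 4 or more with up to 8. The row for subjects is labelled "Number of Treated Subjects". After a pause, "enrollment will not resume until the protocol has been amended".

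Section 7.4.1 makes the DLT window the 4-week infusion of cycle 1 and says it "may also be extended to assess events starting within the window in case the DLT definition is time dependent". Two such definitions are "grade 4 neutropenia lasting more than 5 days, grade 4 thrombocytopenia lasting more than 7 days". Section 5.4 says that 600 µg/day had not been tested, "whereas 2 of 3 subjects treated at the 800 µg/day dose experienced DLTs".

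**The concern.** A subject who started yesterday counts as treated but has contributed almost no DLT information. Once a fifth subject has started, 2 DLTs no longer meet Table 5-1: 3 are needed at 5 or 6 treated, and 4 at 7 or 8. No minimum interval between starts is given, and about 15 sites may enroll (5.2.2). So 2 DLTs in the first 3 or 4 can miss the pause simply because others started before the second DLT was known.

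What remains is DLRT discretion. At stake is whether more subjects start an untested dose that may lie above the plan's target toxicity range, after a result the plan's own model treats as a reason to stop.

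**Working it through.** **1. The plan's boundaries reproduce.** Inputs (Protocol 10.3): a Beta(1,1) prior and intervals 0–0.20, 0.20–0.33 and 0.33–1. With x DLTs in n subjects the posterior is Beta(1+x, 1+n−x). The posterior mass in each interval is divided by its width (0.20, 0.13, 0.67), and the model halts if the over-dosing value is largest. The fewest DLTs that give a halt are 2 at n = 2–4, 3 at n = 5–6 and 4 at n = 7–8, which is Table 5-1.

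**2. What a fifth start does to 2 DLTs.**

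| DLTs / treated | Under | Target | Over | Model and Table 5-1 |
|---|---|---|---|---|
| 2/3 | 0.14 | 0.62 | 1.33 | halt |
| 2/4 | 0.29 | 1.13 | 1.19 | halt |
| 2/5 | 0.49 | 1.65 | 1.03 | continue |

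The 2/5 row is right for five completed outcomes. It is not right when two of the five are still unobserved.

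**3. How often 2 or more of 3 arises.** P(X ≥ 2) = 3p²(1−p) + p³ = 0.104, 0.255 and 0.500 at p = 0.20, 0.33 and 0.50.

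**4. How many have started.** With starts g days apart, subject 3 starts on day 2g and finishes on day 2g + 28. Starts strictly before then number min(10, ⌈(2g+28)/g⌉):

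- g = 3.5: 35/3.5 = 10
- g = 7: 42/7 = 6
- g = 14: 56/14 = 4

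**5. How often the second DLT is known too late.** The documents give neither accrual nor onset times, so these are assumptions. The simulation used 20,000 cohorts of 10 per setting, even spacing, uniform onset and no discretionary stop. The figures are conditional on 2 or more DLTs in the first 3, at true rates of 33–50%:

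| Setting | 3.5 days | 7 days | 14 days |
|---|---|---|---|
| Onset over 28 days, no lag | 82–84% | 38–39% | 0% |
| Same, 7-day confirmation lag | 98–99% | 70–74% | 12–14% |
| Onset within 7 days, no lag | 0% | 0% | 0% |

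Independent runs differ by 1 or 2 points. With random (Poisson) accrual, exactly 2 DLTs in the first 3 and onset over 28 days, the chance is 7%, 21%, 36% and 50% at 1, 2, 3 and 4 subjects a month. With DLTs in the first 3 days it is 1.5% or less at these rates.

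**6. Pause rates.** Onset over 28 days, no lag, pause before the tenth start. The last column is the exact result for Table 5-1 when each outcome is known before the next start.

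| True rate | Rule | 3.5 days | 7 days | 14 days | Outcome known first |
|---|---|---|---|---|---|
| 20% | current | 2.8% | 9.9% | 17.0% | 20.3% |
| | ordered boundaries | 15.5% | 19.7% | 20.3% | |
| 33% | current | 9.5% | 28.4% | 41.1% | 46.6% |
| | ordered boundaries | 36.4% | 45.6% | 47.0% | |
| 50% | current | 24.4% | 58.1% | 73.2% | 78.5% |
| | ordered boundaries | 64.2% | 76.2% | 78.7% | |

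Current-rule rates fall below the last column because of late knowledge. The ordered rule recovers most or all of the difference. It still adds about 3 points at 14 days and a 20% rate because it also catches late DLTs beyond the first 3, such as a late one in subject 4.

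**The case against.** **The plan has safeguards.** Safety data are reviewed continuously and enrollment can be stopped at any time (5.1.1, 10.4.1.1). The DLRT can meet ad hoc (12.3). The sponsor confirms eligibility before first dose and allocates subjects to cohorts (6.3). Cohort 2 starts with three days at 200 µg/day (7.1.1.2) and six days in hospital (7.1.1.4.1). A reader might infer from the bare third bullet that a toxic dose would run unchecked. The documents do not support that: a sponsor who sees 2 DLTs in 3 would very likely act. What stands is that none of these forces a halt.

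**DLTs may come early.** In the first-in-human study, 10 of 12 CRS events were in cycle 1 with onset within 24 hours (3.2.2.4). Early DLTs would nearly always be caught. But the DLTs at 800 µg/day were "1 grade 3 CRS and 1 grade 3 peripheral motor neuropathy", no onset is given for the neuropathy, and duration-based DLTs take days to confirm.

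**Accrual may be slow.** Ten starts at 3.5-day spacing is a fast pace for about 20 subjects at about 15 sites. This is fair, and it is why the point is conditional.

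**The table may mean the first 4 treated.** If so, the gap closes. Section 10.3 speaks of observed data, and the text below Table 5-1 points to the DLT-evaluable definition. But the row is labelled by treated subjects, and a stopping rule should not need interpretation.

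**33% is not over-dosing.** Correct: it is the upper edge of the target interval. Extra pauses at 33% are a cost; benefit should be claimed only above it.

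**Conclusion.** The gap is real but conditional. If the second DLT among the first 3 or 4 becomes known only after a fifth start, Table 5-1 does not force the pause that the plan's model calls for. It needs fast accrual (starts about 7 days apart or less, or a confirmation lag) together with DLTs that are known late. With DLTs known within 7 days and no lag, at the spacings examined, or with even starts at least 14 days apart and no lag, Table 5-1 already catches every 2 of 3.

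At a true rate of 50%, with onset over 28 days and no discretionary stop, the current rule pauses in 24%, 58% and 73% of cohorts at 3.5-, 7- and 14-day spacing, against 78.5% when each outcome is known first. Accrual and onset are assumptions throughout.

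A reader might go further and conclude that cohort 2 must be closed to new starts until the review of the first 3. The documents do not support that as a requirement: the bar for EM subjects shows that such a hold can be written, not that one is needed for everyone. The defect is the table's unclear denominator. Amendment 5 cites termination of the program and no further drug supply, so the point has effect only if cohort 2 still enrolls.

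**What to change.** In Table 5-1 (5.1.1 and the synopsis) and SAP Table 1, add one sentence: the boundaries apply to the first 4, 6 and 8 subjects in order of treatment, whenever their DLTs become known.

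**Cost.** There is no scheduled pause, but more pauses for cause, each needing an amendment. With onset over 28 days they rise at 3.5-, 7- and 14-day spacing as follows:

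- 20% true rate: from about 3%, 10%, 17% to 16%, 20%, 20%
- 33% true rate: from about 10%, 28%, 41% to 36%, 46%, 47%

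The new rates are at or about, or below, the 20% and 47% that the rule gives when outcomes are known in sequence.

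**Do not count only DLT-evaluable subjects instead.** A DLT would count at once but a DLT-free subject only after 28 days. Pauses at a 20% rate would rise to 30%, 29% and 23%, and to 53% at 3.5-day spacing with onset within 7 days.

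**Optional hold.** Barring cohort 2 starts until the first 3 are reviewed is a trade-off. It gives 12%, 13% and 17% pauses at a 20% rate, plus one scheduled stop, assumed to last 4–6 weeks. If used, trigger it once the first 3 have had the chance to finish the infusion, as the cohort 1 reviews do, and let non-evaluable subjects be replaced. As worded, the review needs three full infusions, so one early discontinuation could block it indefinitely.

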**Table 5-1. Rules for Holding Enrollment in Phase 1b**

Number of Dose-limiting Toxicities	≥ 2	≥ 3	≥ 4
Number of Treated Subjects	≤ 4	≤ 6	≤ 8

If the rules for pausing enrollment are met, no further enrollment to the respective dose level/schedule will be allowed until after a careful review of all safety data by the DLRT. Additionally, enrollment will not resume until the protocol has been amended to include additional safeguards for subject safety (eg, modifications to dose level and schedule).

Subjects with EM disease will be able to enroll into cohort 2 after the safety evaluation is complete for 3 subjects with EM disease treated at 400 µg/day.

For definition of the DLT evaluation period and DLT-evaluable subject refer to [Section 7.4.1](#). For details on the mTPI model see [Section 10.3](#).

An investigator will review efficacy data and assess outcomes in accordance with IMWG criteria. Investigator assessments will be used for primary efficacy analysis.

The overall study design is described by a study schema in [Section 2.1](#). The endpoints are defined in [Section 4.1](#).

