### 5.2.1 Replacement of Subjects

Subjects that are not DLT-evaluable may be replaced. A subject is non-DLT-evaluable if subject discontinues treatment for any reason other than a DLT prior to completing the DLT evaluation period (see [Section 7.4.1](#) for DLT details).

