### **10.2 Analysis Sets, Subgroups, and Covariates**

#### **10.2.1 Analysis Sets**

The analysis of all endpoints, unless noted otherwise, will be conducted on the Safety Analysis Set defined as all subjects that are enrolled and receive at least 1 dose of AMG 420. An overall assessment of safety with monotherapy treatment will be conducted on the Monotherapy Safety Analysis Set defined as all subjects that are enrolled in the study and receive at least 1 dose of AMG 420. The analysis of DLT will be restricted to DLT-evaluable subjects (see [Section 7.4.1](#)). The analysis of DOR will be restricted to subjects with a partial response or better. DLT evaluation analysis set includes subjects complete the DLT evaluable period or experienced a DLT any time during the DLT evaluable period. The PK Analysis Set will contain all subjects who have received at least 1 dose of the investigational product and have at least 1 PK sample collected. These subjects will be evaluated for PK analysis unless the number of data points required for analysis is not enough, or significant protocol deviations have affected the data, or if key dosing or sampling information is missing.

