#### **10.3 Adaptive Design**

The rules for halting enrollment, or dose de-escalation, are based on an mTPI design. The mTPI was developed by [Ji et al \(2010\)](#). The mTPI models the probability of toxicity for each dose level using a Bayesian model where each dose level has the same prior on the probability of toxicity, a Beta (1,1). When subjects are treated at the current dose level, the posterior probability of toxicity is updated using the observed data from this level. Enrollment recommendations are made based on this posterior probability of toxicity, using three toxicity probability intervals (TPI).

- Under-dosing TPI: DLT rate from 0 to < 20%
- Target TPI: DLT rate from 20% to 33%

- Over-dosing TPI: DLT rate > 33%

For the current dose level and after adjusting for the width of each TPI interval, if the DLT rate is most likely in the under-dosing TPI or most likely in the target TPI then the recommendation is to continue enrollment at the current level. If the DLT rate is most likely in the over-dosing TPI then the recommendation is to halt enrollment.

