	
protocol-required therapies, and significant treatment-emergent adverse events will also be provided.
 
Dose Limiting Toxicities
 
The analysis of the probability of DLTs will include data from DLT-evaluable subjects (see Section 7.4.1 for definition of DLT-evaluable). The primary analysis will only include DLTs that occur within the first cycle. If DLTs occur outside the first cycle, a sensitivity analysis will be performed where DLTs occurring outside of the specified time interval are included. The number and percentage of subjects reporting DLTs will be evaluated overall and by AMG 420 dose level and part.
 
Clinical Laboratory Tests
 
Clinical chemistry, hematology, and urinalysis data will be listed and reviewed for each subject. Values outside the normal laboratory reference ranges will be flagged as high or low on the listings. Depending on the size and scope of changes in laboratory data, the analyses of safety laboratory endpoints will include summary statistics over time and/or changes from baseline over time. Maximum shifts in grades of selected safety laboratory values between baseline and the worst on-study value may be tabulated.
 
Vital Signs
 
Vital signs data will be listed and reviewed for each subject. Depending on the size and scope of changes, the analyses of vital signs may include summary statistics over time and/or changes from baseline over time.
 
Electrocardiograms
 
Summaries over time and/or changes from baseline over time will be provided for all ECG parameters. Subjects' maximum change from baseline in QTcF will be categorized and the number and percentage of subjects in each group will be summarized. Subjects' maximum post baseline values will also be categorized and the number and percentage of subjects in each group will be summarized. All on-study ECG data will be listed, and select parameters of interest may be plotted.

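### The mandatory enrollment-holding table ends at 8 treated subjects, although cohorts are about 10 plus replacements and its own mTPI model halts at 5 or more DLTs for 9 to 11

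*Protocol*

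**What the plan says.** Protocol 5.1.1 makes the pause mandatory: enrollment to a dose level stops when Table 5-1 is met. It resumes only after a DLRT review and a protocol amendment that adds safeguards. The table's lower row is labelled "Number of Treated Subjects", with columns for up to 4, up to 6 and up to 8 and thresholds of 2, 3 and 4 DLTs. The synopsis table and SAP Table 1 are the same.

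The cohort is longer than the table. Section 5.1.1 plans about 10 subjects at each dose level, and Section 5.2.1 adds: "Subjects that are not DLT-evaluable may be replaced".

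The rule is said to rest on the mTPI model of Protocol 10.3 and SAP 3.3: a Beta(1,1) prior and intervals of 0 to 20%, 20 to 33% and above 33%. The dose is judged by whichever interval is most likely after adjustment for width. That section sets no upper limit on the number of subjects, but its output is a recommendation.

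On who is counted, the model text says: "When subjects are treated at the current dose level, the posterior probability of toxicity is updated". The DLT analysis uses a different set. Section 10.2.1 states: "The analysis of DLT will be restricted to DLT-evaluable subjects". A sentence under Table 5-1 reads "For definition of the DLT evaluation period and DLT-evaluable subject refer to" Section 7.4.1, without saying that the table uses that definition.

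**The concern.** A binding safety rule should cover the whole cohort that it governs. Here the ninth, tenth and any replacement subjects fall outside it. Read literally, five or six DLTs among nine treated subjects trigger no mandatory pause, although the stated model calls for a halt.

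This matters most when DLTs become known late. The DLT window is 4 weeks, so a DLT in one of the first 8 subjects may surface after the ninth has started. By then no column applies.

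Cohort 2 (600 µg/day) is the more exposed. Its only scheduled DLRT review comes after the first 3 subjects; the review at 10 subjects belongs to cohort 1. Section 5.4 says that 600 µg/day was not evaluated in the first-in-human study, where 2 of 3 subjects at 800 µg/day had DLTs.

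**Working it through.** **Inputs.** Prior Beta(1,1) and intervals 0–0.20, 0.20–0.33 and 0.33–1 (Protocol 10.3, SAP 3.3); thresholds from Table 5-1; cohort of 10 (Section 5.1.1).

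**Formula.** With x DLTs in n subjects the posterior is Beta(1+x, 1+n−x). Divide each interval's posterior probability by its width (0.20, 0.13, 0.67). The model halts if the over-dosing value is the largest.

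*Example, 4 of 8.* The posterior is Beta(5,5) and P(rate > 0.33) = 0.860, so over-dosing is 0.860/0.67 = 1.284. Target is 0.925 and under-dosing 0.098. The model halts.

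**Reproducing the table and carrying it on** (target / over-dosing):

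| n | one DLT below the boundary | at the boundary |
|---|---|---|
| 4 | 1 DLT: 2.075 / 0.698 | 2 DLTs: 1.131 / 1.187 |
| 6 | 2: 2.105 / 0.863 | 3: 1.037 / 1.241 |
| 8 | 3: 1.968 / 0.983 | 4: 0.925 / 1.284 |
| 9 | 4: 1.335 / 1.185 | 5: 0.514 / 1.383 |
| 10 | 4: 1.771 / 1.074 | 5: 0.811 / 1.318 |
| 11 | 4: 2.203 / 0.957 | 5: 1.167 / 1.237 |
| 12 | 5: 1.562 / 1.145 | 6: 0.706 / 1.345 |
| 13 | 5: 1.975 / 1.044 | 6: 1.012 / 1.279 |

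The boundaries are 2 (n = 2–4), 3 (5–6) and 4 (7–8), as in Table 5-1, then 5 (9–11) and 6 (12–13), which the table omits. An upper target limit of 1/3 instead of 0.33 gives the same boundaries. The only mismatch below 9 is n = 1: the model halts at 1 of 1 (1.33 against 0.53), while the table needs 2.

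**Effect if every outcome is known before the next enrollment** (treated denominator, no dropout). An added pause needs exactly 3 DLTs in the first 8 without an earlier pause, then DLTs in both subjects 9 and 10. Avoiding an earlier pause means at most 1 DLT in subjects 1–4 and at most 2 in subjects 1–6. Splitting the 3 DLTs over subjects 1–4, 5–6 and 7–8, the allowed sequences number:

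- (1,1,1): 4×2×2 = 16
- (1,0,2): 4×1×1 = 4
- (0,2,1): 1×1×2 = 2
- (0,1,2): 1×2×1 = 2

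The total is 24, so the gain is 24·p³(1−p)⁵·p² = 24·p⁵(1−p)⁵.

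| True DLT rate p | Table as written | With model columns for 9–10 | Gain |
|---|---|---|---|
| 15% | 0.120 | 0.121 | 0.0008 |
| 33% | 0.466 | 0.479 | 0.0127 |
| 50% | 0.785 | 0.809 | 0.0234 |

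All of this gain falls at the tenth subject, when planned enrollment is complete.

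**Effect if DLTs become known late.** Assumptions: one enrollment a week, DLT onset uniform over 28 days, 10% dropout with replacement, treated denominator, columns continued past 10. At a true 50% rate, simulation gives a mandatory pause in 0.55 of trials as written and 0.71 with the model's columns (0.70 in a repeat run). In the repeat run the mean number treated fell by less than 0.1, so the gain is mainly a forced review and amendment, with few enrollments prevented.

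**The case against.** **The gap is covered elsewhere.** Section 5.1.1 refers to Section 10.3, whose halt recommendation has no size limit. Safety data are reviewed continuously, enrollment may be terminated at any time, the DLRT may meet ad hoc, and cohort 1 has a review at 10 subjects. This stands as mitigation, and a reader should not infer that subjects 9 onward are unmonitored. But none of these safeguards fixes a count, and only the table compels a pause and an amendment.

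**The effect is tiny.** That is right when outcomes are known at once. It is not right for the chance of a mandatory pause when DLTs surface late.

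**The stronger reading.** A reader might infer that the table uses the wrong denominator, counting treated instead of DLT-evaluable subjects, and so misses halts. The documents do not support that. All three tables and both model paragraphs say treated, and on that count the table matches the model for every n from 2 to 8. The evaluable set governs the reported DLT analysis, and the pointer under Table 5-1 only locates a definition. For subjects who leave early, Section 7.4.1 adds: "All available safety data for subjects who are non-DLT-evaluable will still be evaluated and considered in DLRT decisions".

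Nor would excluding non-evaluable subjects clearly work better. At an assumed 10% dropout and true rates of 15%, 33% and 50%:

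| Order of events | Treated | Non-evaluable excluded |
|---|---|---|
| Dropout always precedes a DLT | 0.099 / 0.397 / 0.703 | 0.120 / 0.466 / 0.785 |
| DLT always precedes dropout | 0.120 / 0.466 / 0.785 | 0.142 / 0.516 / 0.823 |

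In the first case exclusion restores missed pauses. In the second the treated count loses nothing, and exclusion adds false pauses. Under Section 7.4.1 a subject with a DLT in the window is evaluable, so the second order is possible. The documents give no dropout rate.

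**Conclusion.** The point holds for the length of the table. The mandatory rule and the model behind it agree up to 8 subjects and part at the ninth, inside a planned cohort of about 10. The boundaries follow from the documents alone. The size depends on timing: at most 2.3 percentage points at the three rates examined if outcomes are known at once, and about 16 points (0.71 − 0.55) under the assumed weekly accrual with late DLTs at a true 50% rate. Accrual, onset and dropout are assumptions.

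The denominator is a matter of wording only: the documents should say that the holding rule and the DLT analysis count different subjects, if that is intended.

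The rationale for Amendment 5 records termination of the program and no further drug supply. If enrollment is over, what remains is to report how the rule was applied beyond 8 subjects and on which denominator.

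**What to change.** 1. In Protocol Table 5-1, the synopsis table and SAP Table 1, add the column that the stated model gives: 5 or more DLTs in up to 10 treated subjects. If replacements take a cohort past 10, continue with 5 or more at 11 and 6 or more at 12 to 13.
2. In Protocol 10.3 and SAP 3.3, state which denominator the holding rule uses. Keeping treated subjects needs no change to the existing columns. Say also that subjects still inside the 4-week window count as treated.

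The cost is wording in three tables and two paragraphs, plus slightly more false pauses, each needing an amendment. At a true 15% DLT rate with the treated denominator, the pause probability rises from 0.120 to 0.121 without dropout, or to 0.122 with 10% dropout occurring after any DLT.
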